7.3 Tissue Collection

7.3.1 Fresh Tumor Biopsies

7.3.1.1 Pilot Phase Biopsies

Two biopsies will be collected on Day 4 of the ferumoxytol phase and two biopsies will be collected three days after the first dose of MM-398.

On Day 4 of the ferumoxytol phase, the lesion(s) selected for biopsy will be based on the results of the FMX-MRI obtained on Days 1, 2 and 4. The first core biopsy will be in the region of the tumor that shows the greatest signal change based on FMX-MRI and the second core biopsy will be taken from the region that shows the least signal change based on FMX-MRI.

On Cycle 1 Day 4 of the MM-398 Treatment phase, the lesion(s) selected for biopsy will be based on the results of the FMX-MRI obtained on Days 1, 2 and 4 of the ferumoxytol phase. The post-treatment biopsies will be collected from a previously non-biopsied lesion. The first core biopsy will be in the region of the tumor that shows the greatest signal change on either the T2* or T1 sequences, based on FMX-MRI. The second core biopsy will be taken from the region that shows the least signal change based on FMX-MRI, avoiding obvious areas of necrosis.

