7.3.1.2 Expansion Phase Biopsies

A Post-treatment core biopsy must be collected at 72 h (+/- 1 day) after the C1D1 administration of MM-398. Any lesion that is amenable to a safe multi-pass core biopsy procedure may be selected. Expansion Phase patients in Cohort 3 with central nervous system (CNS) disease only are not required to undergo biopsy; however patients in Cohort 3 with non-CNS disease will be required to submit a biopsy sample, if a core biopsy can be safely obtained from a site of extracranial disease. Three passes should be obtained with the first two passes snap frozen and the third pass, if available, formalin fixed; See Laboratory Manual for details on processing and handling of the biopsy samples. Frozen samples will be used to measure tumor drug (CPT-11) and metabolite (SN-38) levels in order to further establish the mechanism of action of MM-398 and evaluate the relationship with tumor ferumoxytol levels as measured by FMX-MRI. Formalin fixed samples may be used to explore potential markers of sensitivity and resistance to irinotecan other pharmacodynamic markers related to activity of MM-398.

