7.4 Ferumoxytol Magnetic Resonance Imaging

It is anticipated that the MRI parameters will need to be optimized in patients that are enrolled at the beginning of the study and/or in the Expansion Phase, in order to assess any correlations between FMX-MRI signal and TAMs, pharmacodynamic markers, or tumor response. A detailed FMX-MRI protocol is included in the study imaging manual, but briefly, each patient will be required to undergo their FMX-MRIs on the same scanner to reduce inter-scan variability. Each MRI study will be evaluated for image quality and signal characteristics of tumors and reference tissue on T1-, T2- and T2*- weighted sequences. Once a completed set of images from each patient has been received, the images will be loaded onto the viewing workstation for qualitative review and then sent to a quantitative lab for analysis.

During the Expansion Phase, multiple MR images will be collected on Day 1-Day 2 of the ferumoxytol period, at various time points depending on the scan group to which the patient is assigned. The body areas to be scanned will be determined by the location of the patient's disease; detailed instructions are described in the study imaging manual. All patients will have a baseline image acquired prior to the ferumoxytol infusion, and either a second successive image (baseline repeat; Scan Group 1) or a second image occurring 1-4 h after the end of ferumoxytol administration (Scan Groups 2 and 3). All patients will return on Day 2 for a 24 hour (16-24 h window) FMX-MRI using the same protocol and sequences as on Day 1. Patients enrolled into Scan Groups 1 and 2 will require one additional scan either at 24 h or 2 weeks, for a total of 4 scans. Patients will be assigned in an alternating fashion to Scan Groups 1 and 2 before enrollment into Scan Group 3 begins. See Table 14 below for additional details on scan groups and required time points.

Scan Group	N ^a	Baseline	Baseline (repeat)	1-4 h	24 h (16-24 h)	24 h (repeat)	2 wk (+/- 1 Day) Baseline
1	5	Х	Х		Х		Х
2	5	Х		Х	Х	Х	
3	10	Х		Х	Х		

Table 14: Summary of Expansion Phase MRI Scan Groups (Cohorts 1 and 2)

^a Enrollment into Scan Groups 1 and 2 may be increased at the discretion of the Sponsor, in the event that any of the images are not evaluable, or it is determined that more information is needed from the additional scan time points. In this case, enrollment into Scan Group 3 will be decreased by a corresponding number of patients.

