11.3.2.5 Duration of Objective Response (DOR)

DOR is defined as the time from first documentation of response (CR or PR whichever occurs first, by investigator assessment) to the date of disease progression or to death due to any cause, whichever occurs first. Duration of response will be computed only for patients who have CR or PR as best overall response. If progression or death does not occur for a patient with response, the patient's duration of response will be censored in accordance with the rules used for PFS analysis. Duration of objective response will be calculated for all patients that experience documented objective response during the study in weeks as follows:

Duration of DOR (Months) = ((Date of Progression/Death/Censoring - Date of First Recorded CR or PR)+1) *12/365.25

The primary analysis for DOR will be based on the investigator-assessed response. DOR will be summarized by each cohort and overall for expansion phase. The analyses will be performed for efficacy evaluable population.

Imaging - Related:

Pilot Phase:

- **To estimate the correlations between FMX-MRI, TAM levels, and tumor levels of irinotecan and SN-38 with administration of MM-398**
Scatter plot of FMX-MRI vs. tumor SN-38 level, TAM level and irinotecan level will be presented. For FMX-MRI, corrected FMX results across all scanned lesions at the same timepoint for a patient will be used. If there is more than one image data at the same timepoint for a patient, image data will be averaged first before summarizing.
- **To determine the value of FMX-MRI in directing tissue biopsy**
The value of FMX-MRI in directing tissue biopsy will be evaluated by summarizing the feasibility of ferumoxytol (FMX) quantitation in tumor lesions, feasibility of FMX-MRI to identify tumor associated macrophages (TAM), and the relationship assessment between ferumoxytol (FMX) tumor uptake and tumor response.

Expansion Phase

- **To assess the association between deposition, as visualized by ferumoxytol imaging, and measures of efficacy**
The association will be performed on per lesion basis. The analysis will be combined into primary endpoint analysis "The Relationship Between Ferumoxytol (FMX) tumor uptake and tumor response to MM-398" in section 11.1
- **To assess the analytical performance of FMX-MRI measurements and optimize FMX-MRI parameterization**

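### The Pilot plots core drug and TAM levels against patient-level FMX, with no rule pairing each core with the FMX of its own lesion or region

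*SAP*

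**What the plan says.** **Pilot sampling.** Protocol 7.3.1.1 uses FMX-MRI to direct the biopsies. On Day 4 of the ferumoxytol phase, "The first core biopsy will be in the region of the tumor that shows the greatest signal change based on FMX-MRI", and the second core comes from the region of least change. The same greatest/least rule applies three days after the first MM-398 dose, with one addition: "The post-treatment biopsies will be collected from a previously non-biopsied lesion". SAP 11.1 states that irinotecan and SN-38 are measured in cores taken after MM-398 dosing, and SAP 11.2 summarises them per lesion.

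**Pilot analysis.** Correlating FMX-MRI, TAM and tumour drug levels is a Pilot secondary objective (Protocol 3.2, SAP 2.2). In the imaging-related block of SAP 11.3.2.5 the analysis is: "Scatter plot of FMX-MRI vs. tumor SN-38 level, TAM level and irinotecan level will be presented". The FMX value is defined by "For FMX-MRI, corrected FMX results across all scanned lesions at the same timepoint for a patient will be used", followed by "If there is more than one image data at the same timepoint for a patient, image data will be averaged first before summarizing". Protocol 10.9 promises Spearman correlations for the same measurements but does not state the unit of analysis.

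**Expansion.** Protocol 7.3.1.2 says of the biopsy site: "Any lesion that is amenable to a safe multi-pass core biopsy procedure may be selected". It gives one use of the frozen cores as to "evaluate the relationship with tumor ferumoxytol levels as measured by FMX-MRI". The SAP contains no Expansion analysis of FMX against drug level.

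**The concern.** The sampling creates a local contrast within each patient: one core where FMX signal is highest, one where it is lowest, both in an identified lesion. The analysis replaces that contrast with one FMX value per patient and timepoint. Both cores then sit at the same horizontal position on the plot, and that position also reflects lesions from which no tissue was taken.

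The link between FMX and drug deposition is the mechanistic reason for treating FMX-MRI as a possible predictor (Protocol 2.2.3 and 2.3). A flat or weak Pilot scatter could come from the pairing rather than from the biology, and the plot would not show which. Nothing else in the SAP recovers the contrast. The companion objective, the value of FMX-MRI in directing biopsy, is evaluated through feasibility and FMX-response summaries, not by comparing the two cores.

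**Working it through.** The documents give no expected correlation, variance or precision for FMX against drug level, so there is no figure of the plan's own to reproduce. The size below rests on assumptions. The one input from the documents is n = 13, the number of Pilot patients with reported PK (Protocol 2.1.6; 12 to 20 were planned).

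**1. Direction, in closed form.** Let r be the correlation of drug level with the FMX of the biopsied lesion, k the number of lesions averaged (including the biopsied one), and ICC the between-patient share of FMX variance. For a lesion taken at random, the correlation with the patient mean is

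r × √(ICC + (1 − ICC)/k).

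With r = 0.6 assumed:
- ICC 0.2, k = 5: √(0.2 + 0.8/5) = √0.36 = 0.60, so r becomes 0.36.
- ICC 0.5, k = 3: √(0.5 + 0.5/3) = √0.667 = 0.816, so r becomes 0.49.
- ICC 0.8, k = 2: √(0.8 + 0.2/2) = √0.90 = 0.949, so r becomes 0.57.

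The factor is below 1 unless ICC is 1, that is, unless FMX is the same in all lesions of a patient.

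**2. Greatest/least cores with region-level FMX.** Simulation, 20,000 replicates: 13 patients, 4 regions each, FMX = patient effect + region effect with total variance 1, cores at the highest and lowest region, drug = 0.7 × local FMX + noise. Mean Pearson correlation:

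| Between-patient share | Core matched to its region | Patient average |
|---|---|---|
| 0.3 | 0.76 | 0.42 |
| 0.5 | 0.74 | 0.50 |
| 0.7 | 0.72 | 0.57 |

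The matched values exceed the assumed 0.7 because sampling the extremes widens the FMX range. A separate Spearman simulation (6 regions, r = 0.6, ICC 0.2 / 0.5 / 0.8, 3,000 runs) agrees in direction: 0.60 / 0.59 / 0.58 matched, against 0.23 / 0.33 / 0.46 with the patient mean.

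**3. If FMX exists only per lesion.** Add a lesion layer to the model in step 2: 3 lesions of 4 regions, within-patient variance split equally between lesion and region, cores from one lesion. Matching to the lesion mean gives 0.55 / 0.59 / 0.62, against 0.43 / 0.51 / 0.57 for the patient average. The gain is 0.12 / 0.08 / 0.05. With a lesion share of 0.3 or 0.7 of the within-patient variance, the gain runs from 0.04 to 0.10 or from 0.06 to 0.15.

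**4. Precision.** With 13 independent pairs, the approximate 95% interval is tanh(atanh r ± 1.96/√10). For r = 0.60 it is 0.07 to 0.87; for r = 0.46 it is −0.12 to 0.81. A modest dilution can therefore move a visible relationship into one compatible with none.

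**The case against.** **Averaging over lesions is inferred.** The averaging sentence speaks of several images at one timepoint, which could mean repeat scans only. For the Expansion, SAP 11.2 has separate sentences for repeated scans and for multiple target lesions; the Pilot text has no lesion sentence. This stands as an ambiguity. It does not supply what is missing, because under either reading no rule ties a core to its own lesion or region.

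**The larger gain needs region-level FMX.** SAP 11.1 describes quantitation in plasma, tumour lesions and reference tissue, not in subregions. If only lesion values exist, a patient's two post-dose cores still share one FMX value after matching, and the gain is that of step 3. This stands.

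**The consequence is limited.** The Pilot is complete, its tumour drug levels were already reported, and what remains is a descriptive plot for a secondary objective. True, but the change is correspondingly cheap.

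**A stronger reading of the Expansion is tempting.** A reader might infer that free choice of biopsy lesion leaves FMX against drug level impossible to evaluate there, or that Expansion FMX is only ever averaged over target lesions. The documents support neither. Under Protocol 7.4, "The body areas to be scanned will be determined by the location of the patient's disease", so a biopsied lesion that was scanned can be matched. SAP 11.3.2.5 plans a per-lesion association with efficacy and lesion-level performance summaries. FMX against drug level is not a listed Expansion objective, only a stated use of the frozen cores. The imaging and laboratory manuals, which were not available, may already record lesion identity.

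**Conclusion.** The point holds for the Pilot. Tissue was sampled by local FMX signal, but the SAP relates it to an FMX value defined across all the patient's scanned lesions, with no pairing rule. Dilution towards no relationship follows unless FMX is nearly uniform within a patient, and greatest/least sampling presumes that it is not.

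The size is uncertain. Under the stated assumptions the correlation falls from about 0.72–0.76 to 0.42–0.57 relative to region-level matching. Where only lesion-level FMX is available, about 0.05–0.12 is at stake. The number of lesions and regions, the local correlation and the variance shares are all assumed.

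The Expansion part is minor: a stated use of the biopsy has no analysis. The Expansion FMX-response analyses, including the primary one, are unaffected. This should be changed, but it does not threaten the study's main conclusions.

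**What to change.** **SAP 11.3.2.5, Pilot.** Plot each core's irinotecan, SN-38 and TAM level against the corrected FMX of the same biopsied lesion, and of the same region where region-level FMX was quantified. Mark the high-signal and low-signal core of each patient. Keep the patient-level plot as secondary, and state whether it averages over lesions or only over repeat images. If the Spearman coefficients of Protocol 10.9 are reported, state the unit of analysis and allow for two cores per patient.

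**Expansion.** Where the biopsied lesion was quantified on FMX-MRI, record its lesion ID and add the same lesion-matched plot. The choice of biopsy lesion stays with the site on safety grounds.

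**Cost.** SAP wording, retrieval of Pilot biopsy locations, and one Expansion data field if the ID is not already recorded. No extra scan or biopsy is needed. Cores without a quantifiable FMX value drop out of the matched plot, so the number lost should be reported.

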12 SAFETY ANALYSES

Safety analyses will be based on safety population.

The analysis of safety assessments in this study will include summaries following categories of safety and tolerability data collected for each patient:

- Adverse Events
 - AEs and SAEs
 - AEs leading to discontinuation of study drug
 - TEAE
 - Deaths
- Clinical Laboratory Investigations
- Vital signs
- ECG Investigations
- Pregnancies (if any reported)
- Physical exam

Safety analyses will be presented for each safety population in accordance with the respective study periods (see Section 7.6.3). Safety analyses will be summarized by each cohort and overall for expansion phase.

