3 STUDY DESIGN

3.1 General Design and Plan

This study comprises two phases: pilot phase and expansion phase.

Pilot phase will enroll approximately 12 patients, up to 20 in total. The first three patients that are enrolled can have any solid tumor type; however subsequent patients must have NSCLC, CRC, TNBC, ER/PR positive breast cancer, pancreatic cancer, ovarian cancer, gastric cancer, gastro-oesophageal junction adenocarcinoma or head and neck cancer. No more than three patients with ER/PR positive breast cancer can be enrolled in the Pilot Phase and similar restrictions may be placed on other tumor types to ensure a heterogeneous population.

These indications were selected based on data suggesting that these tumor types have high levels of CD68 (tumor associated macrophages) and carboxylesterase enzyme (CES) activity or high levels of deposition, any of which may correlate to MM-398 response.

The Expansion Phase will enroll cohorts of single indications of patients with locally advanced or metastatic breast cancer in 3 cohorts of 10 patients each depending on sub-type of breast cancer:

- Cohort 1: ER and/or PR-positive breast cancer
- Cohort 2: Triple negative breast cancer (TNBC)
- Cohort 3: Breast Cancer (BC) with active brain metastasis

There are four stages to each phase of this study:

- Screening (-28d): patients undergo screening assessments to determine if they are eligible for the study
- Ferumoxytol (FMX) (Day 1 Day 2): patients receive ferumoxytol infusion and undergo required FMX-MRI scans and pre-treatment biopsy (if applicable, see Cohort requirements) prior to receiving MM-398
- MM-398 Treatment (C1D1 progression of disease): patients receive an MM-398 dose of 60 mg/m² every 2 weeks, which should be dose escalated to 80 mg/m² every 2 weeks in subsequent doses depending on patient tolerance, other required assessments, and undergo a post-treatment (MM-398) multiple pass core biopsy
- Follow up (+30d from last dose): patients return to clinic 30 days after their last dose of MM-398 for final safety assessments

Ferumoxytol magnetic resonance imaging (FMX-MRI) will be done for both pilot phase and expansion phase. The schedule for pilot phase FMX-MRI is: pre-dose of ferumoxytol, 1-4 hours post dose and 24 hours post dose of ferumoxytol.

The schedule for expansion phase is outlined in Tables 1 and 2:

Table 1 Summary of Expansion Phase MRI Scan Groups (Cohorts 1 and 2)

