3.2 Treatment Assignment

All patients will be administered a single dose 5 mg/kg of ferumoxytol at Day 1 by intravenous infusion as an imaging agent. MM-398 will be administered at a dose of 60 mg/m² every two weeks starting at Cycle 1 Day 1 during MM-398 treatment phase.

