3.3 Treatment Blinding

This is an open-labeled single treatment arm study. There is no treatment blinding.

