7.5 Planned Subgroups, Interactions, and Covariates

No subgroup analysis is planned.

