 - In the total counts for each severity classification, an individual patient who experiences two AEs of different preferred term of different severities will be included once in the total for each of the appropriate severities.

Tabular summaries will be presented for each cohort and overall for expansion phase. Summaries will include the number and percentage of patients and classified by primary system organ class and preferred term. The following summaries will be reported for AEs, TEAE regardless of drug relationship, TEAE related to study drug, TEAE grade 3 and above regardless of drug relationship, TEAE grade 3 and above related to study drug, serious AEs (SAEs), AE leading to study drug discontinuation, and AE leading to death:

- Overall summary of adverse events will descriptively summarize all adverse events, treatment-emergent adverse events (TEAE), serious adverse events (SAEs), TEAE related to study drug, TEAE with CTCAE grade 3 and above, TEAE related to study drug with CTCAE grade 3 and above, TEAE leading to death, TEAE related to study drug leading to death, TEAE related to study drug leading to discontinuation, and TEAE related to study drug leading to dose adjustment (interruption or decrease).
- Summary of TEAE by system organ class (SOC) and preferred term (PT) by decreasing frequency.
- Summary of TEAE by CTCAE grade, SOC and PT, by decreasing frequency.

- Summary of TEAE related to study drug by SOC and PT, by decreasing frequency.
- Summary of TEAE by CTCAE grade 3 and above, SOC and PT, by decreasing frequency.
- Summary of TEAE related to study drug by CTCAE grade 3 and above, SOC and PT, by decreasing frequency.
- Summary of TEAE related to study drug leading to dose adjustment (interruption or decreased), discontinuation and death by SOC and PT, by decreasing frequency.
- Summary of TEAE related to study drug leading to discontinuation and death by SOC and PT, by decreasing frequency.
- Summary of SAE by SOC and PT, by decreasing frequency.
- Summary of SAE related to study drug by SOC and PT, by decreasing frequency.

Listings of all AEs/TEAEs/SAEs will be presented by treatment group and sorted by patient id, start time, primary system organ class, preferred term and verbatim text for all adverse events recorded during the study, onset day relative to the first treatment date of AEs, date of Resolution, AEs, SAEs, related to study drug.

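### Expansion Phase adverse event tables do not separate patients who started MM-398 at 80 mg/m² from those who started at 60 mg/m², although the start was lowered mid-phase for tolerability

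*SAP*

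**What the plan says.** SAP section 12 sets the grouping for Expansion safety output: "Safety analyses will be summarized by each cohort and overall for expansion phase". Section 12.1 repeats it for adverse events: "Tabular summaries will be presented for each cohort and overall for expansion phase". In SAP 3.1 the three cohorts are ER and/or PR-positive disease, triple negative disease, and disease with active brain metastasis; none is defined by dose. SAP 7.5 adds: "No subgroup analysis is planned".

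On dosing, SAP 3.1 opens its stage list with "There are four stages to each phase of this study". Under that lead it gives an MM-398 dose of 60 mg/m² every two weeks, "which should be dose escalated to 80 mg/m² every 2 weeks in subsequent doses depending on patient tolerance". SAP 3.2 reads: "MM-398 will be administered at a dose of 60 mg/m² every two weeks starting at Cycle 1 Day 1". Neither section says that anyone started at 80 mg/m².

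Two places in the protocol document show that patients did:
- Protocol 2.1.6 reports Pilot Phase pharmacokinetics after 80 mg/m² (n=13).
- The Version 4 to 5 summary of changes says the starting dose went from 80 to 60 mg/m² after a safety review held when 16 patients had enrolled in the breast expansion cohort. It reports gastrointestinal serious adverse events in 36%, diarrhea of any grade in 64% and grade 3 or higher diarrhea in 27%. It expects the lower start to improve tolerability.

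**The concern.** Further characterizing MM-398 safety in metastatic breast cancer is a stated Expansion Phase objective (SAP 2.2). The sponsor changed the starting regimen partway through that phase because of gastrointestinal toxicity. The planned tables put patients from before and after the change into the same cohort and overall columns. A reader could not see event rates under either start, and a reader of the SAP alone would not know that there were two.

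The summary of changes is used here only as a record of what was given. Its difference from the current text is not itself the complaint.

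**Working it through.** **Does any other SAP text supply the split?**
- Section 6 bases the MM-398 safety analyses on the treatment actually received, but names no dose column.
- Section 12.1 says "Listings of all AEs/TEAEs/SAEs will be presented by treatment group". Section 3.3 says "This is an open-labeled single treatment arm study", so treatment group has no defined meaning here, and a listing gives no rates.
- Section 10 summarizes exposure by cycle, including dose reductions, but does not cross-tabulate it with adverse events.
- Section 11.3.2.1 mentions cohorts by dose level for progression-free survival. The term is undefined and does not reach safety.
- Section 7.1 leaves layout to mock shells, which are not in the documents.

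None of these supplies it.

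**How many started at 80 mg/m²?** This is not stated. Sixteen is enrolment at the review. It is not a maximum, because Protocol 12.9 normally requires IRB approval before an amendment takes effect, so further patients may have started at 80. The reported percentages do not fit 16 patients either: the nearest sixteenths are 6/16 = 37.5%, 10/16 = 62.5% and 4/16 = 25.0%. Fractions with a denominator of at most 16 that round to the reported values are:

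| Reported | Fits |
|---|---|
| 36% | 4/11, 5/14 |
| 64% | 7/11, 9/14 |
| 27% | 3/11, 4/15 |

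Eleven is the only denominator up to 16 that fits all three, if they share one (assumption). Exact 95% confidence intervals for grade 3 or higher diarrhea are 6.0% to 61.0% for 3/11 and 7.8% to 55.1% for 4/15.

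**What would the overall column show?** Take 30 patients, the approximate planned Expansion enrolment in SAP section 4. Let n80 be the number starting at 80 mg/m² (11, 16 or 20, assumptions). These are 11/30 = 36.7%, 16/30 = 53.3% and 20/30 = 66.7% of the column. Let p60 be the rate at the 60 start (assumption), with 3/11 as the rate at the 80 start:

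overall = [n80 × 3/11 + (30 − n80) × p60] / 30

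| p60 | n80 = 11 | n80 = 16 | n80 = 20 |
|---|---|---|---|
| 10% | 16.3% | 19.2% | 21.5% |
| 20% | 22.7% | 23.9% | 24.8% |
| 27.3% (no difference) | 27.3% | 27.3% | 27.3% |

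- Largest distance from the 80-start rate: 27.3 − 16.3 = 10.9 points before rounding (n80 = 11, p60 = 10%).
- Largest distance from the 60-start rate: 21.5 − 10 = 11.5 points (n80 = 20, p60 = 10%).
- Using 4/15 in place of 3/11 changes each overall figure by less than 1 point.

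**Without an assumed rate.** Take any event seen in 6 of 30 patients (20%) and, for illustration, an 11/19 split. The same overall cell could be 5/11 and 1/19 (45% against 5%) or 2/11 and 4/19 (18% against 21%). The planned table cannot tell these apart.

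**The case against.** The absence of the split is not in dispute. The case for leaving it out is as follows.

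- **The groups overlap.** Patients starting at 60 mg/m² are meant to escalate if they tolerate it, doses are reduced for toxicity, and events are counted to 30 days after the last dose. A grade 3 event at 80 mg/m² after escalation would fall in the 60-start column. This stands: the split cannot be a dose comparison or show that tolerability improved. It does not count against a descriptive display. Group size does not either, since the planned cohort columns hold about 10 patients each.
- **The illustration rests on chosen inputs.** The safety population may exceed 30, because patients who are not pharmacodynamically evaluable may be replaced yet stay in the safety tables; the shares above would then change. The rate of 3/11 is also very imprecise. With n80 = 11 and p60 = 10%, the gap between the 80-start rate and overall is 19/30 × (p80 − 10%), which runs from −2.5 to +32.3 points over the interval 6.0% to 61.0%. Both points are fair, and the figures should be read as illustrations.
- **Protocol 12.9 also allows immediate change for an imminent hazard.** It does, but nothing shows that route was used. The number who started at 80 remains unknown.
- **SAP 3.1 and 3.2 simply restate the current protocol, whose safety section requires no dose split.** This is largely right for the Expansion Phase. Between current texts, the firm conflict is the 60 mg/m² description for each phase against 80 mg/m² in the Pilot. It alters no adverse event count.
- **Post-hoc analyses are allowed.** They are. But the SAP cites protocol Version 6.0 of April 2017, and the start was changed in Version 5 of November 2016. A regimen change already known should be prespecified.

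**Conclusion.** The point holds. It is certain that no planned Expansion safety table shows rates by starting dose, that the start was lowered from 80 to 60 mg/m² for tolerability during that phase, and that SAP 3.1 and 3.2 describe only the 60 start.

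The consequence is less certain. Under the assumptions above, the overall grade 3 or higher diarrhea figure lies 0 to 11 points from the 80-start rate and 0 to 12 points from the 60-start rate. It could lie further off given the imprecision of 3/11, and the true difference may be nil. The Pilot patients affect these tables only if the phases are pooled, which SAP 5.2 permits.

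No planned count is wrong. The weakness is that the safety summary conceals a change made for safety. It should be corrected because the remedy is cheap and serves a stated objective.

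**What to change.** 1. Reconcile SAP 3.1 and 3.2 with Protocol 2.1.6 and the dosing history, stating which starting dose applied to which patients. This takes no view on which dose is right.
2. Within the overall Expansion Phase, add descriptive columns by actual starting dose (80 and 60 mg/m², taken from the dosing data) to the exposure, treatment-emergent event, grade 3 or higher, serious event and discontinuation tables. Keep the cohort and overall columns. Footnote that the split is descriptive only: the groups are small, overlap through escalation and dose reduction, and are confounded with calendar time.

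The cost is two columns in about five tables, from data already collected, plus a text correction. The drawback is that readers may over-read a difference between small groups of as yet unknown size. The disease-cohort columns would still mix the two starts.
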